## 13. Trial Procedures

### 13.1. Summary of Trial Assessments

	Baseline (up to 6 weeks prior to randomisa- tion)	Day 1 (at least 5 days prior to Cycle 1 Day 1)	Dose evaluation visit 1	Dose evaluation visit 2	Dose evaluation visit 3	Cycle 1, Day 1	Cycle 2, Day 1	Cycle 3, Day 1	Cycle 4, Day 1	Cycle 5, Day 1	Cycle 6, Day 1	Trial Completi- on Visit b)
Consent a)	X											
Demographics	X											
Medical History	X											
Cancer history	X											
Performance Status	X											
NYHA Class	X											
Concomitant medications b)	X	X	X	X	X	X	X	X	X	X	X	X
Physical Assessment (height and weight)	X											
Blood Pressure	X		X	X	X	X	X c)	X				
Troponin T	X d)						X c)	X				
Troponin I	X						X c)	X				
U+Es	X		X	X	X		X c)	X				
eGFR	X											
Pregnancy test e)	X											
Echocardiogram f)	X											X
Eligibility check	X											
Randomisation	X											
Enalapril (intervention group only)		X	X	X	X	X	X	X	X	X	X	
Adherence to enalapril (intervention group only)		X	X	X	X	X	X	X	X	X	X	X
Standard care adjuvant chemotherapy (all patients)						X	X	X	X	X	X	
Adverse Events		X	X	X	X	X	X	X	X	X	X	X
Buccal swab for future research	X											
Blood sample for future research	X							X		X		X
Acceptability of trial interventions assessment									X			X

- a) Consent must be taken prior to baseline assessments and confirmation of eligibility, and within 6 weeks of randomisation.
- b) A list of all medication currently being taken by the patient, including total daily dose, should be recorded at baseline; changes and new medications must be recorded throughout the trial.
- c) All blood samples, including those for troponin T and I, MUST be taken before the next dose of chemotherapy is given; these and blood pressure monitoring can be performed up to 72 hours in advance of the day of chemotherapy.
- d) Troponin T at baseline will be used to assess eligibility
- e) Women between the ages of 18 and 50 must have a negative pregnancy test at baseline, and prior to randomisation and use adequate contraception from consent, throughout the trial.

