#### 13.2.7. Blood Pressure

Blood pressure (BP) will be assessed at baseline, prior to taking any blood samples. BP needs to be assessed whilst the patient is sitting. If the first reading provides a systolic value greater than 160mmHg, the test should be repeated on two further occasions, with the patient quiet and seated. If white coat hypertension is suspected, ambulatory BP monitor may be used to avoid inappropriate exclusion from the trial. Severe hypertension on ambulatory BP is defined as 150/95.

All patients will have their BP measured in the same way within 72 hours prior to day 1 of each cycle of chemotherapy and also at the trial completion visit.

For those patients randomised to receive enalapril, BP will also be measured on each of the days that they attend for a dose evaluation visit.

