#### **13.2.9. Urea and Electrolytes (U&Es)**

U&Es (Urea, Na+, K+ and Creatinine) will be assessed at baseline, at each dose evaluation visit (enalapril arm only), and within 72 hours prior to the intended day 1 at the start of chemotherapy at cycle 2, 3, 4, 5, 6 and at one month after the last epirubicin dose.

Samples will be collected, processed and analysed in accordance with local hospital practice, with the results recorded in the eCRF. These blood samples are often taken and tested routinely, if this is the case, and they fit within the windows for the trial, repeat tests specifically for the trial are not needed.

If serum creatinine levels increase by 30 µmol/L over 48-96 hours, or increases to >1.5 times the baseline value, the clinical judgement of the Principal Investigator should be sought, and/or the Chief Investigator, to confirm the action to be taken, which may require a temporary or permanent halt to enalapril (for those in the enalapril group).

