##### **14.6.1. Dosing visit day 1**

Patients will be dispensed 2.5mg enalapril BD as their starting dose to begin taking that day.

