## 16.5. Adverse Event Reporting

All AEs will be recorded in the patients' medical notes and on electronic case report forms. AEs will be recorded from the day of randomisation until the last visit or until withdrawal, with the exception of adverse events considered related to enalapril, which will be followed until resolution, a stable outcome or death.

All AEs will be assessed for severity, causality, and seriousness and expectedness by an Investigator. All events will be reviewed by the Independent Data Monitoring and Ethics Committee (IDMEC) as part of their ongoing assessment of safety.

Patients should be asked about any adverse events at each visit.

Where an AE fulfils the criteria for a reportable SAE as part of this trial, this will be reported immediately to NCTU (within 24 hours of the research team becoming aware of the event) who will inform the Sponsor and Chief Investigator. Should the SAE form be incomplete at the time of the initial report, follow-up information should be provided as it becomes available. The relationship to the IMP should be assessed by the Investigator at the site, and they will also assess expectedness in relation to the approved RSI.

Exceptions for SAE reporting include hospitalisation for:

- Routine treatment or monitoring of the studied indication not associated with any deterioration in condition
- Treatment which was elective or pre-planned, for a pre-existing condition not associated with any deterioration in condition
- Any admission to hospital or other institution for general care where there was no deterioration in condition

In the event that a SUSAR is fatal or life-threatening, the sponsor will inform the MHRA and the REC within 7 days. In the event that a SUSAR is non-life-threatening, the sponsor will inform the MHRA and the REC within 15 days.

All Principal Investigators will be informed of all SUSARs throughout the trial, as they occur.

SAEs and SUSARs should be reported to NCTU within 24 hours

[[contact]](mailto:[contact])

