### 17.1. Statistical Analysis

Data cleaning and analysis will be provided by staff within NCTU and Durham University. Primary analysis will follow intention to treat principles with patient data analysed according to randomisation and irrespective of intervention received; other analysis groups such as per-protocol may be considered subsequently. Every effort will be made to retain and include all patients who are part of the trial.

A full statistical analysis plan (SAP) will be developed for the outcome measures and agreed with the IDMEC and Chief Investigator prior to any analysis being undertaken.

Outcome data will be analysed at the end of the study, no interim analyses is planned.

The primary analysis of presence or absence of cardiac troponin T will be assessed using Fisher's exact test. Analysis of the secondary endpoints will be dependent upon the nature of the specific endpoint and data structure; global longitudinal strain (GLS) and left ventricular ejection fraction (LVEF) will be analysed as a change from baseline using a t-test to compare intervention and control groups.

Cardiac troponin I data will also be analysed using Fisher's exact test. Changes in cardiac troponin T and I will also be analysed as a continuous variable. Additional analysis of the primary endpoint will be performed using logistic regression to account for baseline factors (regimen and HER2 status). Adverse events data will be analysed using cross-tabulation. Sensitivity analysis will also be performed for adherence to the protocol.

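### Adverse events, BP and U&Es are checked more often on enalapril by design, so an unrestricted cross-tabulation is likely to overstate the between-arm difference for laboratory- and BP-defined events

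*Combined protocol and SAP*

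**What the plan says.** Section 16.5 sets the collection rule: "Patients should be asked about any adverse events at each visit". It applies one recording window to both arms: "AEs will be recorded from the day of randomisation until the last visit or until withdrawal". Events judged related to enalapril are followed beyond that.

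In the schedule (section 13.1) the "Adverse Events" row is marked in 11 columns: Day 1, dose evaluation visits 1 to 3, day 1 of cycles 1 to 6, and completion. The row carries no arm label, but other sections tie the early visits to enalapril:

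- Section 13.2.7: "For those patients randomised to receive enalapril, BP will also be measured on each of the days that they attend for a dose evaluation visit".
- Section 13.2.9 schedules U&Es at baseline, "at each dose evaluation visit (enalapril arm only"), before cycles 2 to 6, and one month after the last epirubicin dose.
- Section 14.6.1, on Day 1: "Patients will be dispensed 2.5mg enalapril BD as their starting dose to begin taking that day". No control-arm activity is described for that day.

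Sections 14.6.3 and 14.6.4 make dose evaluation visits 2 and 3 depend on what was done at the visit before. Section 14.6.5 adds a BP and U&E check after any re-introduction or dose adjustment.

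The analysis in section 17.1 is one sentence: "Adverse events data will be analysed using cross-tabulation". The same section defers detail to a full SAP, still to be developed.

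**The concern.** Adverse events and adverse reactions to enalapril are secondary outcomes (section 9.3), and section 7.5 says the results should inform whether enalapril is given routinely. The trial is open-label, and one arm is questioned and tested more often than the other. A table of all recorded events by arm then mixes two things: what enalapril does, and how often someone looked.

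This matters most for events that exist only if a test is done. The severity scale in section 16.1.7 counts asymptomatic laboratory findings as possible grade 1 events. Section 14.5 lists hyperkalaemia and renal impairment among enalapril's known effects. These are the events a reader of the safety table will look for, and they are where the arms are least comparably observed.

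**Working it through.** The plan states no figure for the adverse event comparison, so there is none to reproduce.

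**1. Scheduled adverse event contacts (sections 13.1, 14.6)**

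- Shared: 6 cycle visits + 1 completion visit = 7.
- Enalapril, minimum: 7 + Day 1 + dose evaluation visit 1 = 9.
- Enalapril, full titration: 7 + Day 1 + 3 dose evaluation visits = 11.
- If controls also attend Day 1: 8 against up to 11.

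Dose-adjustment checks can take the enalapril count higher.

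**2. Post-baseline measurements (sections 13.2.7, 13.2.9)**

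| | Control | Enalapril |
|---|---|---|
| U&Es | cycles 2–6 + completion = 6 | 6 + up to 3 = up to 9 |
| BP | cycles 1–6 + completion = 7 | 7 + up to 3 = up to 10 |

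Controls have no trial-scheduled U&E between baseline and the sample before cycle 2. A transient rise in potassium or creatinine in that interval can be found by scheduled trial testing in one arm only. Recall at a later visit cannot recover it.

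**3. Reported symptoms: size under a constant daily hazard**

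Assumptions: no drug effect; an event recorded in 30% of controls between cycle 1 and completion; titration counted as extra observed time on enalapril.

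- Cycle 1 to completion: 5 × 21 + 28 = 133 days.
- Daily hazard: −ln(0.70)/133 = 0.00268.
- Titration: three intervals of 2 to 5 days = 6 to 15 days.
- Enalapril proportion: 1 − 0.70 × exp(−0.00268 × T).

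| Titration T | Enalapril | Excess, no control recall | Excess, 50% recall |
|---|---|---|---|
| 6 days | 31.1% | 1.1 points | 0.6 points |
| 15 days | 32.8% | 2.8 points | 1.4 points |

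With full recall the excess is zero. At 85 per arm, 1.1 to 2.8 points is about 1 to 2 patients.

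**4. Near-universal chemotherapy effects**

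Assume a 10% risk in the titration period, a 95% risk later and no control recall. Enalapril: 1 − 0.90 × 0.05 = 95.5%, against 95%, an excess of 0.5 points.

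**5. The opposing effect**

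Section 14.6.2 withdraws some enalapril patients from the study at dose evaluation visit 1, and recording then largely stops. Such a patient has 2 adverse event contacts against 7 for a control. In the step 3 model, with no control recall, the withdrawn fraction w that cancels the excess is excess ÷ (enalapril proportion − proportion recorded before withdrawal):

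- T = 6, withdrawn on day 2 (0.5% recorded): 0.0112/(0.3112 − 0.0053) = 3.7%.
- T = 15, withdrawn on day 5 (1.3% recorded): 0.0276/(0.3276 − 0.0133) = 8.8%.

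For symptoms, early withdrawal of roughly 4% to 9% would therefore remove the inflation, and more would reverse it.

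**The case against.** The strongest counter-argument is that the observation window is the same in both arms. Controls asked at cycle 1 can report anything since randomisation, so extra contacts need not mean extra events. For symptoms that stands, and it is why the estimate is small. It does not stand for potassium or creatinine, which need a sample, or for an asymptomatic BP reading. Routine local blood tests may narrow the gap, but the plan does not schedule them for controls before cycle 1.

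A reader might infer a much larger effect by giving every contact the same chance of yielding an unrelated event. At 5% per contact, 7 contacts give 1 − 0.95^7 = 30%, and 9 to 11 contacts give 37% to 43%. The documents do not support that model: it treats a visit 2 to 5 days after the last one like a visit after a three-week cycle. Nor is it right to speak of a false-positive rate, because section 17.1 plans a cross-tabulation and names no test for adverse events.

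Two further points stand. Some early excess will be real drug effect, since the titration visits look for hypotension, hyperkalaemia and creatinine rise. Replacing the full comparison with shared visits alone would discard that effect and drop patients withdrawn during titration, which would favour enalapril. And the SAP to come may supply a visit rule; section 17.1 leaves this open and does not choose a biased analysis.

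**Conclusion.** The concern holds in a limited form. Ascertainment is unequal by design (7 against 9 to 11 contacts; 6 against up to 9 U&E checks), and section 17.1 has no safeguard. The Day 1 count rests on inference from its dispensing purpose.

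For laboratory- and BP-defined events, overstatement of the enalapril-minus-control difference is likely. Its size cannot be fixed, because the documents give no event rates. For symptoms, inflation is probably 1 to 3 points for a 30% event under the stated assumptions, less with recall, negligible for near-universal chemotherapy effects, and open to cancellation or reversal by early withdrawal.

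A reader might infer that the table will overstate harm across the board. The documents do not support that: the direction is not certain for symptoms, and part of any early excess would be genuine.

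**What to change.** In section 17.1 or the SAP:

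1. Keep the full adverse event table from randomisation for all randomised patients, with per-patient denominators and withdrawals shown by arm.
2. Add a between-arm table limited to shared visits.
3. Base the between-arm comparison of potassium and creatinine events on the shared U&E measurements (cycles 2 to 6 and completion), and of BP events on the shared BP measurements (cycles 1 to 6 and completion).
4. Tabulate events first found at Day 1, titration or dose-adjustment visits separately, as enalapril tolerability. Classify them by visit type, not by date relative to cycle 1: titration can take 6 to 15 days, while Day 1 need be only 5 days before cycle 1, so titration visits can fall after it.

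No visit or clinical procedure changes. The cost is one or two extra tables. The shared-visit table omits early titration effects and patients withdrawn during titration, so it must be read beside the full table.

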## **18. Structure and Duration of the Trial**

The total duration of this trial is anticipated to be 30 months; this comprises recruitment ending 20 months after the start of the grant. Patients will be followed for a minimum of 6 months following the start of their adjuvant chemotherapy. The trial will randomise 170 patients from participating centres in England. The final 4 months will comprise final data cleaning, analysis, report writing and dissemination of research findings.

The duration of trial participation for individual patients will be from the day of consent until the last follow-up assessment following adjuvant chemotherapy or withdrawal. Where a patient withdraws, but there is a study related adverse event, this will be followed until resolution, a state of persistence or permanence, or death. All participants will be asked to consent to longer-term follow up using routine data.

### **18.1. Definition of the end of the trial**

The end of the trial will be defined as the last assessment for the last patient at one month following the last epirubicin dose in the trial.

### **18.2. Early Trial Cessation**

If the Sponsor, Chief Investigator, NCTU, IDMEC, TSC, or TMG discover conditions arising during the trial that indicate the trial should be stopped, this action may be taken. The TSC carries the responsibility for deciding if the trial should be stopped early. Conditions likely to warrant study termination include, but are not limited to:

- Futility: the trial has no prospect of reaching its recruitment within the given time frame
- There is a substantial change in understanding/scientific advancement meaning that continuation of the trial is inappropriate
- Safety: overwhelming evidence for harm makes continuation non-viable

### **18.3. Remuneration**

No financial or material incentives will be given to participants, however reasonable travel expenses will be given for participants who return to the hospital for visits that are additional to standard care but required per the protocol.

## **19. Quality Control and Assurance**

### **19.1. Risk Assessment**

NCTU, in collaboration with the Sponsor, has assessed the risk of this trial and will review the risk level regularly throughout the trial.

### **19.2. Trial Registration**

This trial will be registered with the International Standard Randomised Controlled Trial Number (ISRCTN) database and on the European clinical trials database (EudraCT).

### **19.3. Site Initiation and Training**

Site Initiation Visits (SIV) at each participating centre will be performed by the Chief Investigator or his delegate and by representatives from NCTU. SIVs should be conducted once appropriate approvals are in place, but may occur earlier if required. Recruitment must not start until all appropriate approvals are in place.

Specific training will be given to centre staff on use of the randomisation system, eCRF system and other trial related processes as appropriate.

### **19.4. Centre Monitoring and Auditing**

The trial will be monitored by Newcastle Clinical Trials Unit (NCTU) and representatives from NCTU will visit the centres periodically, and in accordance with a trial-specific monitoring plan. NCTU representatives will review the quality of the data to confirm that the trial is being run in accordance with the protocol.

NCTU representatives will review the Case Report Forms of patients who are randomised for this study, and will compare these directly to the medical notes and source data (a process known as source data verification (SDV)). SDV of consent and full SDV of all data fields will occur for a proportion of patients who enter the trial, chosen at random. All signed consent forms will also be reviewed.

At monitoring visits NCTU staff will also discuss the conduct of the trial with the local trial team and review the Investigator Site File.

In addition, the study may be evaluated by an auditor or government inspector, who will also be allowed access to all case report forms, source documents, study files and all study facilities.

Protocol compliance will be monitored by NCTU. Prospective, planned deviations or waivers to this protocol are not allowed. Any accidental protocol deviations will be documented on the relevant CRFs and reported to NCTU as soon as possible. Frequent and repeated protocol deviations are unacceptable and potentially constitute a serious breach.

### **19.5. Blinded Endpoint Review**

This trial has blinded endpoint analysis of the primary outcome measure (troponin T) and of the echocardiogram and troponin I secondary outcome measures.

Central laboratories in Newcastle upon Tyne and Teesside will analyse the troponin T and I, respectively. Laboratory staff will be blinded to trial allocation.

All echocardiograms will be sent securely to the Core laboratory, based at The James Cook University Hospital for review and reporting. The Core laboratory team will be blinded to trial allocation.

### **19.6. Serious Breaches**

A serious breach will be reported to the Sponsor as soon as it is identified. The sponsor will notify the MHRA and REC within 7 days of becoming aware of the serious breach. Serious breaches are defined as a breach of the protocol which is likely to affect to a significant degree the safety or physical or mental integrity of a trial patient or the scientific value of the trial.

### **19.7. Ethics and Regulatory Compliance**

#### **19.7.1. Good Clinical Practice**

The trial will be run according to the conditions and principles of ICH GCP, and in accordance with relevant UK legislation and the protocol.

#### **19.7.2. Approvals**

The trial will not start until a favourable opinion has been given by an NHS REC, and both MHRA and HRA approval has been granted.

### **19.8. Information Governance and Confidentiality**

The information collected as part of this trial will be stored securely both electronically and on paper and kept confidential. Data will be used according to the provision of the 1998 Data Protection Act, and applicable new regulations, and individuals will not be identifiable through any reports or publications that result from the trial.

Patients will be assigned a unique trial identifier at screening. All paper study files and documents, including personal data and each patient's consent form will be retained at the participating NHS Trust in a locked office prior to secure archiving at the end of the study. Electronic trial records will be kept on secure NHS servers with access restricted to the study team; these will be securely archived at the end of the trial. Research data will be transferred to Newcastle Clinical Trials Unit, Durham University, and to Newcastle University for analysis in collaboration with the clinical trial team.

Data will be entered onto an electronic case report form for each patient. The data will be validated as defined in the study-specific data management SOP. Data will be stored on secure servers that are external to both the sponsoring NHS Trust and to Newcastle and Durham Universities. Personal identifiable data on these servers will be encrypted and all data will have access restricted to authorised personnel and be password protected. Data extracted for review during the course of the trial, and for archiving at the end of the trial, will be stored securely in restricted access areas of the Newcastle and Durham University server systems. This data will be accessible to the full research team and to Newcastle Clinical Trials Unit, Durham University, and Newcastle University staff, as well as in summary form to members of the TSC, IDMEC, and TMG. There may be occasions when TSC or IDMEC members may need unique study ID, age, gender and ethnicity when reviewing data; where possible data will be aggregated or fully anonymised.

The data stored electronically in the database will contain the month and year of birth, gender, and ethnicity, and assigned trial number for each patient, but no other personal identifiable data.

Echocardiograms for each patient will be sent to the Echo Core Laboratory for review in a blinded manner. These data will be included in the final research data set for analysis.

Blood samples collected during the trial may be analysed by local and central laboratories. Additional samples will be taken and stored for use in further research.

Consent from individual patients will enable scan data, along with their other trial research data, and sample data, to be used in future research following the end of PROACT.

Patients who withdraw from the trial will have all data collected up until the point of withdrawal included in the study, except where withdrawal is due to a trial related AE. In this event the patient will be followed until a stable outcome is achieved. Where a patient who has withdrawn agrees, data to answer the primary endpoint of the study can be collected; this will be recorded and the data included in the trial analysis.

An auditor or regulatory inspector may access trial data as required.

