## 9. Trial Design

### 9.1. Summary

A prospective, randomised, open-label, blinded end-point, superiority trial in patients undergoing anthracycline-based adjuvant chemotherapy for breast cancer. Patients will be randomised in a 1:1 ratio to enalapril (intervention) or control (standard care). The trial will evaluate the effectiveness of enalapril in preventing cardiotoxicity detected by cardiac troponin T.

The trial is anticipated to take 30 months to complete and will randomise 170 patients due to receive anthracycline-based adjuvant chemotherapy for their breast cancer at participating NHS Trusts.

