### 12.2. Withdrawal of participants

Patients may withdraw from the trial at any time if they wish to, without giving reason and without any adverse consequences for their ongoing clinical management. Patients in the intervention arm will need to stop taking enalapril maleate on the day they withdraw, and return all unused drug to the clinical research team.

All patients will be made aware of their right to withdraw from the study, and this information will be included in the patient information sheet.

Patients should be withdrawn from the trial by the clinical team if:

- the patient suffers unacceptable side effects caused by enalapril maleate;
- the patient becomes ineligible between randomisation and commencement of chemotherapy;
- the patient becomes pregnant or there is evidence that a patient fails to use adequate birth control;
- the patient has disease recurrence.

Data and blood samples for troponin assessment collected up to the point of withdrawal will be kept and used in the analysis of the trial.

Patients will be asked upon withdrawal:

- whether further data can continue to be collected from their medical records;
- whether samples collected for future research may still be analysed;
- whether they may be approached in future research connected to the trial.

This information will be captured on a withdrawal form, to be stored in the ISF and a copy of which sent to NCTU (by email), this will also be captured in the eCRF.

Data from patients who withdraw will remain in the overall analysis; however, dependent on the stage of withdrawal, then further patients may be recruited to ensure that the sample size is reached.

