#### **13.2.12. Echocardiogram**

Cardiac function will be assessed via transthoracic echocardiography (TTE) at baseline, and 4 weeks following the last epirubicin dose.

All echocardiograms will be assessed by a Core Laboratory, led by [name], and [name] at The James Cook University Hospital. Images will be transferred from the study centre to the Core laboratory in accordance to the PROACT Echocardiogram Manual. [name], [name], and their team, will be blinded to the arm of the study to which patients are allocated.

Local reporting of the TTEs will be as per local hospital practice; the data reported by the Core laboratory (including GLS and LVEF) will be recorded in the eCRF and will be analysed as part of the secondary outcomes for the trial.

The PROACT Echocardiogram Manual provides further guidance to all centres involved in the study, detailing the number, quality and types of images to be acquired, and details of how to send these to the Core Laboratory. Heart rate and sinus rhythm will also be recorded at the time of the echocardiograms.

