## 17. Statistics

### 17.1. Sample Size

Audit data from 36 patients and 143 samples, showed a positive troponin T in 47% of patients who received  $>300\text{mg/m}^2$  of anthracycline in a six-cycle regimen. As a sensitive marker of cardiac cell death, we expect troponin to be “turned off” if enalapril is effective. There are other potential causes of an elevated troponin during chemotherapy that are accounted for in the sample size calculation. There is clinical consensus that a rate of 20% in elevated troponin would fully account for other causes such as infection.

Assuming alpha of 5%, and 90% power, 140 patients are needed to detect a reduction in the proportion of patients with cardiac troponin T present from 47% to 20% using a two-sided Fisher's exact test.

There is consensus within the clinical community that, a large effect size will be necessary to convince the clinical community to change the pathway of care for these patients.

Allowing for attrition, the trial will recruit and randomise 170 patients.

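### The plan makes no provision for the completion echocardiogram in withdrawn patients, so GLS and LVEF would in practice be compared only in patients with both scans, and the loss can differ by arm

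*Combined protocol and SAP*

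**What the plan says.** **Collection after withdrawal.** Section 18 runs each patient's participation to the last follow-up assessment or to withdrawal. Section 19.8 keeps what was collected before withdrawal and adds: "Where a patient who has withdrawn agrees, data to answer the primary endpoint of the study can be collected". Section 12.2 lists a separate question put to withdrawing patients, "whether further data can continue to be collected from their medical records", which is not limited to any endpoint.

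**The echocardiographic outcomes.** Section 13.2.12 states: "Cardiac function will be assessed via transthoracic echocardiography (TTE) at baseline, and 4 weeks following the last epirubicin dose". The values analysed are those reported by the Core laboratory from images acquired under the trial's echocardiogram manual. Section 17.1 (Statistical Analysis) states that "global longitudinal strain (GLS) and left ventricular ejection fraction (LVEF) will be analysed as a change from baseline using a t-test". It names no method for missing scans. It describes the primary analysis as following intention to treat, promises every effort to retain patients, and defers detail to a full SAP.

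**Routes out of the trial.** Section 12.2 has the clinical team withdraw a patient for unacceptable side effects of enalapril. Section 14.6.2 couples permanent discontinuation at dose evaluation visit 1 with withdrawal from the study.

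**Attrition.** Section 17.1 (Sample Size) says "Assuming alpha of 5%, and 90% power, 140 patients are needed" and then "Allowing for attrition, the trial will recruit and randomise 170 patients". It gives no percentage.

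**The concern.** A patient who leaves before the completion visit has no second scan and therefore no change score. The troponin T outcome has a stated route to continued collection after withdrawal; the scan does not. A site following the text has no stated basis for inviting a withdrawn patient back for it, even one willing to return for the primary endpoint.

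The t-test would then compare patients with both scans, which is not the comparison of randomised groups that intention to treat implies. The withdrawals for enalapril side effects, and those under the visit 1 rule, can arise only in the enalapril arm. If such patients differ in cardiac prognosis, or gain less from the drug, the comparison shifts. The synopsis presents these measures as bearing directly on patient outcomes, so they will carry weight in interpretation.

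Troponin I is affected less. It is sampled at the same visits as troponin T, and section 12.2 keeps troponin samples taken before withdrawal. The gap there concerns later samples.

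**Working it through.** **1. The plan's own figures.** The inputs in section 17.1 are two-sided alpha 0.05, power 0.90, and a change "from 47% to 20% using a two-sided" Fisher's exact test, with 1:1 allocation from section 9.1.

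- Uncorrected n per arm = [1.960·√(2 × 0.335 × 0.665) + 1.282·√(0.2491 + 0.16)]² / 0.27² = 62.1, rounded up to 63 (126 in total).
- With continuity correction, n = (62.1/4)·[1 + √(1 + 4/(62.1 × 0.27))]² = 69.3, rounded up to 70 (140 in total).
- Exact enumeration of Fisher's test at 70 per arm gives power 0.908.

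The stated 140 is reproduced. The implied margin is (170 − 140)/170 = 30/170 = 17.6%, or 15 of 85 per arm if split equally.

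**2. Precision for GLS and LVEF, in SD units.** SE = √(1/n₁ + 1/n₂). The difference detectable at 90% power is (1.960 + 1.282) × SE.

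| Patients with both scans | SE | Detectable difference |
|---|---|---|
| 85 v 85 | 0.153 | 0.50 SD |
| 70 v 70 | 0.169 | 0.55 SD |
| 55 v 85 (all 30 losses in one arm) | 0.173 | 0.56 SD |

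The SE rises by about 10% (0.169/0.153 = 1.10), so loss of precision is modest. Bias matters more.

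**3. Bias from differential loss, no drug effect.** Let a and b be the shares withdrawn before the scan in the enalapril and control arms. Let D be the amount, in SD, by which withdrawn patients do worse than those who stay. Each arm's observed mean exceeds its full mean by its share times D, so the bias in the difference is D × (a − b), in enalapril's favour when a > b. Divide by SE = √(1/[85(1 − a)] + 1/[85(1 − b)]). The documents give none of a, b or D. The splits below are assumptions chosen to average 17.5%, close to the implied margin.

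| a / b | SE | Bias, D = 0.25 | Bias, D = 0.5 |
|---|---|---|---|
| 20% / 15% | 0.169 | 0.0125 SD = 0.07 SE | 0.025 SD = 0.15 SE |
| 25% / 10% | 0.170 | 0.0375 SD = 0.22 SE | 0.075 SD = 0.44 SE |
| 30% / 5% | 0.171 | 0.0625 SD = 0.37 SE | 0.125 SD = 0.73 SE |

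For scale, a two-sided 5% test with a bias of k standard errors rejects with probability Φ(−1.96 + k) + Φ(−1.96 − k). At k = 0.07 this is 0.029 + 0.021, about 5%. At k = 0.73 it is 0.109 + 0.004, about 11%.

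**4. Bias when the drug works only in those who continue.** Assume a 0.5 SD benefit in continuers, none in the 17.6% who stop, and 70 per arm with both scans. The effect over all randomised patients is 0.5 × (1 − 0.176) = 0.41 SD. Patients with both scans show 0.50 SD. The gap is 0.088 SD, or 0.088/0.169 = 0.52 SE.

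**The case against.** Several stronger readings are tempting, and the documents do not support them.

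- **That 19.8 forbids other collection.** It is permissive and contains no word of limitation, and section 12.2 asks about medical records without naming an endpoint. The fair reading is silence about the scan. That silence still matters: section 18 ends participation at withdrawal, and no section describes how a scan done in routine care would reach the Core laboratory. Section 19.8 also follows patients withdrawn for a trial-related adverse event until a stable outcome, but it does not say that this includes the completion scan.
- **That 17.6% is the plan's withdrawal rate or ceiling.** It is the spare margin for losses of any kind against the primary-endpoint sample size. The true share could be lower or higher, and section 12.2 allows further recruitment.
- **That every cardiac secondary outcome is lost.** Troponin I collected before withdrawal is retained.
- **That every patient who stops enalapril for intolerance leaves the trial.** Sections 14.6.3 to 14.6.5 describe dose reductions, temporary halts and stopping the drug without stating a trial exit.

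Two further objections carry weight. The bias figures rest wholly on assumed inputs, the low end is negligible, and the scenario in step 4 gives no benefit to patients who took enalapril for several cycles before leaving. And a full SAP is promised, which could set out how missing scans are handled. It cannot recover scans that were never taken.

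**Conclusion.** The concern holds as a gap in provision. Followed as written, the plan gives withdrawn patients no completion echocardiogram, and the named t-test then uses only patients with both scans. The loss can be unequal by arm because two of the routes to withdrawal depend on taking enalapril.

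The size is unknown. If the full 30/170 margin were withdrawal before the scan, with prognosis gaps of 0.25 to 0.5 SD and splits from 20%/15% to 30%/5%, the bias is about 0.07 to 0.73 SE; the continuers-only scenario falls within that range at 0.52 SE. These results show that the effect could run from trivial to enough to disturb a borderline result. They do not forecast it. The point touches secondary outcomes only and is worth acting on because the remedy is cheap.

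**What to change.** In section 19.8, and in matching terms in section 12.2, replace the reference to the primary endpoint with wording such as: *Where a withdrawn patient agrees, data for the primary and cardiac secondary endpoints can be collected: troponin T and troponin I from the same serum sample, and the scheduled completion TTE, sent to the Core laboratory. These data enter the comparison by randomised group whether or not enalapril was taken.* The schedule's existing condition that the scan precede any Herceptin would continue to apply. Sections 12.2 and 19.8 should then agree on what a withdrawing patient is asked. The SAP should say how scans that are still missing will be handled.

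This concerns data collection and leaves the clinical rules for stopping enalapril as they are.

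The cost is an amendment to the protocol and consent wording, possibly a substantial one, and one attendance for each withdrawn patient who agrees. No new procedure is needed, since the scan is already scheduled for every randomised patient and both troponins use the same sample. The benefit is limited to those who agree to return.
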